5.4.2. Storage, Dispensing and Investigational Product Accountability

Upon receipt at the investigational site, INP103, benserazide and placebo must be stored at controlled room temperature in light-resistant containers (not refrigerated or frozen), as specified in the pharmacy manual. A record will be maintained by the investigational site, which will account for all dispensing and return of any used and unused INP103, benserazide, or placebo. At the end of the study, INP103, benserazide and placebo will be reconciled, and a copy of the record given to the study monitor.

Upon completion of the study, any surplus supplies will either be destroyed at the site in accordance with the site's standard operating procedures (SOPs) and upon receipt of written approval from the Sponsor with evidence of destruction supplied to the study monitor or will be returned to an appropriate storage facility as indicated by the Sponsor.

The Investigator will be fully responsible for the security, accessibility, and storage of all drug products whilst they are at the investigational site.

Following training on the use of INP103 and the placebo by an authorized Impel NeuroPharma trainer, the Investigator will then be responsible for the education of study staff in the correct administration of the products.

Further information about the storage, preparation and administration of drug products can be found in the Investigator's Brochure, Pharmacy Manual and Instructions for Use.

6. STUDY PROCEDURES

Study visits should be completed as indicated in the Study Schedule located in [Table 1](#).

Blood samples for L-dopa PK should be collected at the time points and within the windows designated in [Table 1](#)

Sites should prioritise in the following order: PK blood draws; UPDRS/Dyskinesia assessments; other safety assessments. All procedures should be completed as close to the prescribed/scheduled times as possible and may be conducted in sequence by the sites according to their standard practice. Due to variability in assessment length, assessments collected out of window, with the exception of PK samples and UPDRS, will not be considered deviations. Any non-scheduled procedures required for urgent evaluation of safety concerns take precedence over all scheduled routine procedures.

6.1. Medical History

Medical history will be recorded at Screening (Visit 1).

6.2. Demographics

Date of birth, age (calculated), sex, ethnicity, and race will be recorded at Screening (Visit 1).

6.3. Body Weight and Height/ Body Mass Index

Body mass index (BMI) is calculated by dividing the subject's body weight in kilograms by the subject's height in meters squared ($BMI = kg/m^2$). Body height (centimetres) and body weight (kilograms) will be measured at Screening (Visit 1). Body weight and height will be obtained with the subject's shoes and jacket or coat removed.

6.4. Safety Assessments

This study primarily assesses the safety and tolerability of INP103. Safety will be determined by evaluating Physical Examination findings, ECGs, vital signs, clinical laboratory parameters, concomitant medication usage and AEs. If deemed necessary, additional safety measurements will be performed at the discretion of the PI and/or Sponsor's Medical Monitor.

6.4.1. Nasal Inspection

Nasal inspection will be performed before and after the single dose at times noted in [Table 1](#) and on an ongoing basis throughout the study. Any signs of inflammation, ulceration, contact bleeding, oedema, or other abnormalities will be reported.

6.4.2. Overall Dyskinesia Assessment

Following dosing with INP103 or placebo, at each inquiry into AEs, or when conducting the MDS-UPDRS Part III assessment, the Investigator or suitably trained designee (who is familiar with rating dyskinesias), must assess the overall level of dyskinesia, based on the scale below. The most severe grade of dyskinesia observed at that time point, as determined by the same assessor (Investigator or suitable trained designate), and as per usual practice, will be recorded.

0 (Normal)	No dyskinesia.
1 (Slight)	Dyskinesias impact on a few activities.
2 (Mild)	Dyskinesias impact on many activities.
3 (Moderate)	Dyskinesias impact on activities to the point that the patient usually cannot perform some activities.
4 (Severe)	Dyskinesias impact on function to the point that the patient usually does not perform activities.

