3.18 CONSTANCY OF REST TREMOR

SCORE

Instructions to examiner: This item receives one rating for all rest tremor and focuses on the constancy of rest tremor during the examination period when different body parts are variously at rest. It is rated purposefully at the end of the examination so that several minutes of information can be coalesced into the rating.

- 0: Normal: No tremor.
- 1: Slight: Tremor at rest is present \leq 25% of the entire examination period.
- 2: Mild: Tremor at rest is present 26-50% of the entire examination period.
- 3: Moderate: Tremor at rest is present 51-75% of the entire examination period.
- 4: Severe: Tremor at rest is present $>$ 75% of the entire examination period.

DYSKINESIA IMPACT ON PART III RATINGS

- A. Were dyskinesias (chorea or dystonia) present during examination? No Yes
- B. If yes, did these movements interfere with your ratings? No Yes

HOEHN AND YAHR STAGE

- 0: Asymptomatic.
- 1: Unilateral involvement only.
- 2: Bilateral involvement without impairment of balance.
- 3: Mild to moderate involvement; some postural instability but physically independent; needs assistance to recover from pull test.
- 4: Severe disability; still able to walk or stand unassisted.
- 5: Wheelchair bound or bedridden unless aided.

Part IV: Motor Complications

Overview and Instructions: In this section, the rater uses historical and objective information to assess two motor complications, dyskinesias and motor fluctuations that include OFF-state dystonia. Use all information from patient, caregiver, and the examination to answer the six questions that summarize function over the past week including today. As in the other sections, rate using only integers (no half points allowed) and leave no missing ratings. If the item cannot be rated, place UR for Unable to Rate. You will need to choose some answers based on percentages, and therefore you will need to establish how many hours generally are awake hours and use this figure as the denominator for "OFF" time and dyskinesias. For "OFF dystonia", the total "Off" time will be the denominator. Operational definitions for examiner's use.

Dyskinesias: Involuntary random movements

Words that patients often recognize for dyskinesias include "irregular jerking", "wiggling", "twitching". It is essential to stress to the patient the difference between dyskinesias and tremor, a common error when patients are assessing dyskinesias.

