4.2 FUNCTIONAL IMPACT OF DYSKINESIAS

Instructions to examiner: Determine the degree to which dyskinesias impact on the patient’s daily function in terms of activities and social interactions. Use the patient’s and caregiver’s response to your question and your own observations during the office visit to arrive at the best answer.

Instructions to patient [and caregiver]: Over the past week, did you usually have trouble doing things or being with people when these jerking movements occurred? Did they stop you from doing things or from being with people?

- 0: Normal: No dyskinesias or no impact by dyskinesias on activities or social interactions.
- 1: Slight: Dyskinesias impact on a few activities, but the patient usually performs all activities and participates in all social interactions during dyskinetic periods.
- 2: Mild: Dyskinesias impact on many activities, but the patient usually performs all activities and participates in all social interactions during dyskinetic periods.
- 3: Moderate: Dyskinesias impact on activities to the point that the patient usually does not perform some activities or does not usually participate in some social activities during dyskinetic episodes.
- 4: Severe: Dyskinesias impact on function to the point that the patient usually does not perform most activities or participate in most social interactions during dyskinetic episodes.

B. MOTOR FLUCTUATIONS

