11.7. Other Safety Measures

11.7.1. Dyskinesia Examination

The result of dyskinesia examination will be presented in data listing. The Dyskinesia Grade (Grade 0 to 4) will be summarized by cohort and treatment group and protocol specified collection time point, using frequency tabulations.

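### The 0–4 dyskinesia scale has no grade for visible dyskinesia that affects no activity, and no planned table uses the Part III yes/no dyskinesia items that would cover the gap

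*Protocol*

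**What the plan says.** Protocol 3.1 and SAP 3.2.1 single out the dyskinesia assessment within the primary safety endpoint.

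Protocol 6.4.2 supplies the instrument. After dosing, at each adverse event inquiry or Part III assessment, a trained assessor records "The most severe grade of dyskinesia observed at that time point". Grade 0 is "No dyskinesia", grade 1 (Slight) is "Dyskinesias impact on a few activities", and grade 4 (Severe) applies when the effect is such that "the patient usually does not perform activities".

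Protocol Appendix 4 contains a closely similar scale, MDS-UPDRS item 4.2. Its grade 0 reads "No dyskinesias or no impact by dyskinesias on activities or social interactions". It belongs to Part IV, described there as "the six questions that summarize function over the past week including today".

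The Part III form in the same appendix ends with two yes/no items outside the score. The first is "Were dyskinesias (chorea or dystonia) present during examination"; the second asks whether the movements interfered with the ratings.

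On analysis, SAP 11.7.1 says "The result of dyskinesia examination will be presented in data listing" and adds frequency tables of the 0–4 grade by cohort, treatment group and time point (Table 14.3.7.1). SAP 10.1 builds the motor score from items 3.1 to 3.18 only. None of the tables in SAP 17.2.2 is assigned to the two Part III dyskinesia items.

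**The concern.** A grading scale for a safety outcome should have a place for every state the assessor may see. This one does not. An assessor who sees chorea that disturbs nothing must contradict the wording of grade 0 by entering 0, or the wording of grade 1 by entering 1.

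The time frame is also mixed. The grade should describe a single time point, but grades 3 and 4 turn on habitual behaviour, which an assessor in clinic 30 minutes after a dose cannot observe directly.

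What is at stake is the readability of Table 14.3.7.1. Each active group has six subjects (up to nine in Cohort 4), there are five sites, and SAP 8.1 makes no site adjustment. A difference between groups in the frequency of grade 1 or higher could partly reflect rater convention. Separately, the interference item tells the reader which Part III totals, and so which values of the motor endpoint, were hard to rate. As planned, that information reaches no table.

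**Working it through.** The documents state no dyskinesia rate and no figure for this measure, so there is nothing to reproduce. The check is a comparison of texts, followed by simple arithmetic for scale.

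**Step 1: the two scales side by side.**

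| State | Protocol 6.4.2 | MDS-UPDRS item 4.2 (Appendix 4) |
|---|---|---|
| No dyskinesia | 0 | 0 |
| Visible, no effect on activities | no grade | 0 |
| Effect on a few activities | 1 | 1, if all activities are still usually performed |
| Effect on many activities | 2 | 2, same qualifier |
| Some activities prevented | 3, with *usually* | 3, with *usually* |
| Activities not performed | 4, with *usually* | 4, for most activities, with *usually* |
| Time frame | one time point | past week |

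The second row is the gap. The protocol requires a full MDS-UPDRS pre-dose at Visit 3 (7.4.1). Sites therefore score dyskinesia without impact as 0 on item 4.2 on the same day that 6.4.2 reserves 0 for its absence.

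**Step 2: what else is collected.** Part III is done pre-dose as part of the full scale. Post-dose it is done at 15, 30, 45, 60, 90 and 120 minutes in Cohorts 1–3 and at 30, 60, 90 and 120 minutes in Cohort 4 (Protocol 7.4.3). The form's presence item needs no judgement about activities. The time points common to all cohorts are 30, 60, 90 and 120 minutes.

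**Step 3: what one ambiguous subject does to the table.** Group sizes come from Protocol 3.

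- Active group of 6: 1/6 = 16.7 percentage points.
- Cohort 4 at its maximum of 9 active: 1/9 = 11.1 points.
- Pooled placebo, 4 cohorts × 2 = 8: 1/8 = 12.5 points.
- If 2 of 6 had such dyskinesia (an assumption): 0/6 = 0%, 1/6 = 17% or 2/6 = 33%, depending on the coding alone.

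**Step 4: chance that a group shows any case.** Let *p* be the rate of visible dyskinesia without impact and *q* the chance that a rater enters grade 1 or higher. Both are assumed. The probability that at least one of six subjects is tabulated at grade 1 or higher on this account is 1 − (1 − *pq*)^6.

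| *p* | *q* = 0.5 | *q* = 1 |
|---|---|---|
| 0.10 | 1 − 0.95^6 = 27% | 1 − 0.90^6 = 47% |
| 0.20 | 1 − 0.90^6 = 47% | 1 − 0.80^6 = 74% |
| 0.33 (1/3) | 1 − (5/6)^6 = 67% | 1 − (2/3)^6 = 91% |

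At *q* = 0 every entry is 0%. The result depends heavily on *q*, which the protocol leaves open.

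**The case against.** The best defence is that the text leans towards grade 1. Grade 0 says there is no dyskinesia, so an assessor who sees some should not enter it, and grade 1 is the lowest remaining grade. Assessors must be familiar with rating dyskinesia, and the protocol calls for the same assessor. This makes grade 0 less likely and limits drift within a subject. It does not settle the convention between raters or sites, because grade 1 still states a condition that the subject does not meet.

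Second, the event need not be lost. Protocol 8.2.1 allows a mild adverse event that does not affect daily activities, and SAP 11.1 tabulates treatment-emergent events by severity. SAP 8 lists everything in the database. These routes are real but partial. Protocol 8.4 does not make an abnormal assessment an adverse event in itself, 8.2 excludes expected fluctuations of existing disease that do not worsen, and a listing is not a comparison by treatment.

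Third, the protocol does not say that its scale comes from item 4.2. That is an inference from wording, and item 4.2 itself admits observation at the visit. Part III also has subjects tap, rise and walk, so some effect on activity can be seen in clinic. The gap exists whatever the scale's origin, and *usually* affects only grades 3 and 4.

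Fourth, a group of six gives a 16.7-point step for any yes/no item. That is correct: the arithmetic shows how coarse the table is, not how often miscoding would occur.

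**Conclusion.** The point holds as a gap in the instrument and a missed use of information that the Part III form asks for. The 0–4 scale is not exhaustive, its upper grades mix time frames, and the two Part III items appear in no planned table. Each ambiguous subject moves a group's proportion by 11 to 17 percentage points. How many such subjects there will be cannot be derived from the documents.

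A reader might infer more, and three stronger readings should be set aside:

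- *Mild dyskinesia is the expected event, so the main signal will be miscoded.* The documents give no expected rate or severity. Exclusion criterion 1 removes only severe dyskinesia that would interfere with assessments and says nothing about what one dose produces.
- *Such events will go unrecorded.* Adverse event reporting and the listings may capture them.
- *Dose escalation is compromised.* The criterion in Protocol 3 concerns related serious or severe adverse events, and the Safety Monitoring Committee reviews adverse events (8.1). A choice between grades 0 and 1 does not in itself trigger it. SAP 11 also plans no inferential safety testing.

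The conclusion assumes that the two Part III items are captured in the eCRF. The casebook cited in SAP 2 is not among the documents, so this is unconfirmed.

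**What to change.** Amend SAP 11.7.1 and Table 14.3.7.1 before database lock:

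1. Tabulate both Part III items (dyskinesia present; interfered with ratings) by treatment at pre-dose and at 30, 60, 90 and 120 minutes. Show 15 and 45 minutes for Cohorts 1–3 only.
2. Add the number of subjects with dyskinesia absent pre-dose and present at any of the four common post-dose time points. Counting over all post-dose examinations would give Cohorts 1–3 six chances of detection against four in Cohort 4, and the pooled placebo group would mix the two schedules. The new count also supplies a comparison with baseline, which Protocol 12.3 promises for the dyskinesia assessment and SAP 11.7.1 does not provide.
3. Flag Part III totals rated with interference in Listing 16.2.6.2.3.
4. Keep the 0–4 table through 240 minutes and Day 7, because the Part III items stop at 120 minutes on the dosing day. Add a footnote that the scale has no anchor for dyskinesia without activity impact.

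Do not reword the 6.4.2 scale mid-study. That would put two scales into the pooled placebo group, blur the comparison of Cohorts 2 and 4, and require a protocol amendment with ethics approval.

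The cost is a few extra table rows and a listing flag. The sponsor must first confirm that both items are in the eCRF; if they are, no new data collection is needed.

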6.4.3. Physical Examination

Complete physical examinations will be performed by a licensed physician at the time-points specified in [Table 1](#).

Complete physical examinations include: general appearance, head, ears, eyes, throat, dentition, thyroid, chest (heart, lungs), abdomen, skin, neurological, extremities, back, neck, musculoskeletal, and lymph nodes. A nasal inspection will also be completed ([Section 6.4.1](#)).

Directed physical examination (120 to 180 minutes post-dose only) includes: head, ears, eyes, throat, chest (heart, lungs), abdomen, skin, musculoskeletal, and lymph nodes and any pertinent system based on any prior findings.

Physical examinations may be performed at various unscheduled time-points if deemed necessary by the PI.

6.4.4. Mini Mental Status Examination (MMSE)

Subjects should have an MMSE score of >25 documented within the previous 36 months. If MMSE score is not available, the assessment should be conducted by the Investigator during Screening to confirm eligibility.

6.4.5. Vital Signs

Subjects should be resting in a supine position for at least 3 minutes prior to and during vital signs measurement obtained. Blood pressure, heart rate, respiration rate and temperature should be measured when the subject is supine. Immediately following supine vital signs assessments, blood pressure only will be measured again when standing. When the time of vital signs measurement coincides with a

blood draw, the vital signs will be taken after the scheduled blood draw, while ensuring the blood draw is within the window specified in the protocol. When vital signs and other safety assessments occur at the same timepoints, clinic staff may follow the sequence of their usual standard practice.

Additional vital signs may be performed at other times if deemed necessary.

6.4.6. Electrocardiogram Monitoring

A 12-lead ECG will be taken at the time-points delineated in [Table 1](#). Table 1 ECGs (heart rate, PR, RR, RS, QRS, QT and assessment of clinical significance of abnormalities) will be performed with subjects in a recumbent position. Subjects must be in this position for at least 3 minutes before the reading is taken.

All ECG tracings will be reviewed by the PI or his/her designate and classified as normal; abnormal, not clinically significant or abnormal and clinically significant. If possible, the ECG electrodes will remain in place until the last ECG in the domiciled period.

When the time of ECG monitoring coincides with a blood draw, the ECG will be taken after the scheduled blood draw while ensuring the blood draw is within the window specified in the protocol. When ECG monitoring coincides with other assessments, clinic staff may follow the sequence of their usual standard practice.

6.4.7. Laboratory Investigations

Safety laboratory tests (haematology, serum chemistry, and urinalysis [UA]) will be performed at the time-points specified in [Table 1](#) and analysed by an appropriately certified central laboratory.

Medically indicated laboratory tests (emergency or unscheduled tests) should be conducted at the local laboratory.

6.4.7.1. Haematology and Serum Chemistry

A blood sample will be taken from each subject for haematology and serum chemistry analysis at the time-points delineated in [Table 1](#) (see [Appendices 1](#) and [2](#) for parameters to be tested). Additional clinical laboratory tests may be performed at other times if deemed necessary.

6.4.7.2. Urinalysis

A urinalysis test (dipstick) will be performed for each subject by a central laboratory. Urine analysis will be performed at Screening (Visit 1), and when the subject is admitted to the institution on Day 0 and other times according to the Study Schedule (see [Appendix 3](#) for parameters to be tested). Urine microscopy will be performed in the event of an abnormal dipstick.

A urine pregnancy test will be performed at Visit 2, 3 and 4 as specified in the Study Schedule.

6.4.8. MDS-UPDRS

A full MDS-UPDRS (Parts I-IV) will be assessed at Visit 1 (screening) and on arrival at clinic for dopaminergic responsiveness assessment (Visit 2). Subjects will omit their usual anti PD medication from 22:00 the previous evening and should arrive at the clinic for both Visits 2 and 3 in an OFF state. Once a full MDS-UPDRS assessment has been undertaken, at visit 2 they will take their usual regular PD medication as well as any additional rescue medication they would usually take for OFF episodes at home followed by MDS-UPDRS Part III (motor) assessment at +15, +30, +45, +60, +90 and +120 minutes post PD medication for Cohorts 1, 2 and 3, and +30, +60, +90, and +120 minutes for Cohort 4. Subjects demonstrating a 30% improvement in MDS-UPDRS Part III at visit 2 will be deemed dopamine responsive and will be eligible for randomization.

A full MDS-UPDRS (Parts I-IV) will also be assessed prior to dosing on Visit 3 and during follow-up (Visit 4).

Further (post-dose) MDS-UPDRS III assessments (motor scores) will occur at the time points delineated in the Study Schedule in [Table 1](#).

MDS-UPDRS criteria and questions are provided in [Appendix 4](#).

6.4.9. Subject Questionnaire

At 120 up to 180 minutes after dosing with INP103 or placebo, subjects will be asked the questions in the questionnaire provided in [Appendix 6](#). This should follow all other assessments.

6.5. Pharmacokinetic Assessments

6.5.1. Sampling and Processing

An intravenous cannula will be inserted prior to all medication dosing at Visit 3 to enable baseline PK and subsequent blood draws to be performed.

Blood samples for PK analysis of L-dopa (and carbidopa in Cohort 4) will be obtained, according to the site's SOPs, within 15 minutes prior to INP103 or placebo dosing and at the time-points (related to INP103/placebo dosing), and within the windows, delineated in the Study Schedule in [Table 1](#).

The actual collection time of each sample must be recorded in the source data documentation, on the collection tube and in the electronic case report form (eCRF). The allowed time deviation window for blood sample collection is + 1 minute for samples up to 30 minutes, and then \pm 2 minutes for the 44, 59, 89 and 119 minutes sample time points (following INP103/placebo dosing) before a deviation is recorded. PK blood draws will precede UPDRS assessments. Due to variability in

assessment length, assessments collected out of window, with the exception of PK samples and UPDRS, will not be considered deviations

The Sponsor will supply complete written instructions for handling, processing, storage, and shipping of PK samples in the laboratory manual prior to study initiation.

